3.4.4 Analysis of patient reported outcomes

For the analysis of quality of life assessments/patient reported outcomes (PRO), the scoring of the questionnaires will be handled as specified by the instrument developers.

To assess rate of missing data, a table of completion rates for each questionnaire at each scheduled assessment will be created. The table will include number of patients eligible for PRO assessment and number of patients with complete PRO assessment data, completion will be defined by each instruments scoring guidelines.

Change in individual scores/scales from baseline will be summarized descriptively at each visit. For FACT-Lymphoma scores, repeated measures analysis will also be used.

Change in ECOG Performance Status

The ECOG performance score will be summarized descriptively by visit. The summary will include the number and percent of patients at each reported value. A shift table including the number and percent of patients will also be produced by visit of baseline vs. post-baseline scores.

Change in FACT-Lym scores

The FACT-Lym questionnaire consists of a total of 42 questions contributing to 5 subscales (i.e., physical well-being, social/family well-being, emotional well-being, functional well-being and lymphoma subscale) which in turn contribute to three total sum scores, namely

FACT-Lym Trial Outcome Index (TOI), FACT-General (FACT-G) total score and FACT-Lym total score. More details on the questionnaire and derivation of the score can be found in Section 16.1.9.

Data from FACT-Lymphoma scores will be analyzed in the three sum scores and one subscale LymS. Change and percent change from baseline to each scheduled visit when the FACT-Lymphoma scores were collected will be calculated. The scores will be summarized descriptively by visit. The change from baseline score at each time point will be estimated by using repeated measurement analysis for patients with at least one post-baseline scale score. Patients without baseline value will not be considered in the analysis and baseline is the data collected from the last visit prior to or at Day1.

Time on treatment time will be treated as a discrete variable to allow for a nonlinear relationship between PRO scores and time. Time, DIPSS status and baseline score (as a covariate) will be included in the model as fixed effects, while the patient-specific intercept will be included as a random effect.

DIPSS status will be calculated as per the criteria given in section 3.11.3

Change in FACIT Fatigue scores:

Data from FACIT-Fatigue scores will be analyzed in the sum scores. Change and percent change from baseline to each scheduled visit when the FACIT Fatigue scores were collected will be calculated with the data collect from the last visit prior to and at Day 1 as the baseline. The scores will be summarized descriptively by visit.

Responder Analysis and Time to first improvement:

The proportion of patients showing improvement will be estimated for ECOG performance score, the three FACT Lym sum scores and one subscale LymS and FACIT Fatigue scale.

The improvement (i.e. the responder) will be defined by the upper limit of the MID. Patients with the best possible score at baseline will be excluded from this analysis because their HRQoL cannot be further improved.

Additionally, the proportion of patients achieving response (HRQoL) by the lower limit of MID will be presented by visit.

Responders and non-responders for a PRO endpoint will be defined based on change from baseline scores using pre specified cutoff points. Patients with an improved PRO score compared to baseline, for which the magnitude of the change was at least the cutoff value, will be classified as responder; otherwise, non-responder.

To define PRO responder, the cutoff points are chosen based on minimum important difference from literature as listed in the following table.

PRO Score	Range	MID	Responder Cutoff
FACT -G total	0-108	3-7 ^c	7
ECOG performance status	0-5	NA	1
FACT-Lym subscale	0-60	2.9-5.4 ^d	5.4
FACT-Lym TOI	0-116	5.5-11 ^d	11

PRO Score	Range	MID	Responder Cutoff
FACT-Lym Total	0-168	6.5-11.2 ^d	11.2
FACIT - Fatigue	0-52	3	3

^a Kvam et al., 2010; ^b Osoba et al., 1998; ^c Webster et al., 2003; ^d Carter et al., 2008.

The median time to first improvement will be estimated using Kaplan Meier method for ECOG performance score, the three FACT Lym sum scores and one subscale LymS and FACIT Fatigue scale. The time to improvement event will be determined based on upper bound of the MID. The time to improvement is calculated from the date of first study drug administration.

Patients, who prematurely discontinued the study drug, will be censored at the date of their last assessment before study discontinuation.

Patients with no baseline score will be censored at study day 1.

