1.1 Overview of myelofibrosis and myeloproliferative neoplasms and current treatment options

Myelofibrosis (MF) is a clonal hematologic neoplastic disease characterized by the presence of megakaryocyte proliferation and atypia, usually accompanied by either reticulin and/or collagen fibrosis ([Tefferi A \(2008\)](#)), splenomegaly, anemia, and debilitating constitutional symptoms that include fatigue, weight loss, pruritus, night sweats, fever, and bone, muscle, or abdominal pain ([Mesa RA, Niblack J, Wadleigh M, et al \(2007\)](#), [Abdel-Wahab OI, Levine RL \(2009\)](#)). MF can either be primary in origin (primary myelofibrosis, or PMF) or result from progression of polycythemia vera or essential thrombocythemia vera ([Tefferi A \(2008\)](#)). The median age at diagnosis of MF is approximately 65 years. Patients with myelofibrosis have shortened survival that ranges from a median of approximately 2 years to 11 years depending on the presence of certain risk factors that define their risk category including age, anemia, leukocytosis, etc.

Several prognostic risk scores that are based on survival outcomes have been developed in MF to better define treatment choices for physicians and therefore improve patient management. The International Prognostic Scoring System (IPSS) was developed by the International Working Group for Myeloproliferative Neoplasms Research and Treatment (IWG-MRT) ([Cervantes F, Dupriez B, Pereira A, et al \(2009\)](#)). The IPSS is used at diagnosis and employs five hematologic and clinical variables (age, leukocytosis, anemia, peripheral blood blasts and constitutional symptoms) to stratify patients in a low, intermediate-1, intermediate-2 and high-risk category. The dynamic IPSS (DIPSS) was subsequently developed to be used for patients evaluated after MF diagnosis ([Gangat et al 2011](#)). The DIPSS relies upon the same five variables as IPSS but utilizes the predictive value of selected cytogenetic abnormalities. These scoring systems are expected to facilitate categorizing patients to different risk groups, and thus assist physicians in recommending optimal treatment management plans.

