Day of visit		-28 to -1	-7 to -1	Day 1	Day 28	Day 56	Day 84	Day 168	Day 252	Day 336				
Vital signs (D)	7.4/8.2.4	X	X		X	X	X	X	X	X	X	X	X	X
Height (D)	7.3/8.2.5	X												
Weight (D)	7.4/8.2.5	X	X		X	X	X	X	X	X	X	X	X	X
Full neurologic and cardiac assessment for fедратиниб pretreated patients (S)	7.3/8.2.6	X												
Measurement of spleen by palpation (D) (See Section 8.3.1.1)	7.4	X	X		X	X	X	X	X	X	X	X	X	X
ECOG performance status (D)	7.4	X	X		X	X	X	X	X	X	X	X	X	
12-lead ECG (D) (See Section 7)	7.4	X	X		X		X			X				
Adverse events (D)	7.4/8.2.1	X	X	X	X	X	X	X	X	X	X	X	X	X
Quality of Life	7.4/8.3.2													
FACT-Lym version 4 (D)	7.4/8.3.2		X		X		X	X		X				
FACIT-Fatigue Subscale (D)	7.4/8.3.2		X		X		X	X		X				
Medical resource utilization (D)	3.3.4/7.4		X		X	X	X	X	X	X				
Dispense Investigational Product (D)	7.4			X	X	X	X	X	X	X	X			
Drug Accountability Assessment (D)	6.5.4/7.4				X	X	X	X	X	X	X	X	X	
Assess Investigational Product Compliance (D)	7.4/11.4				X	X	X	X	X	X	X	X		
INC424 Dose Administration	6.1/7.4			X	X	X	X	X	X	X	X	X	X	

Evaluation	Reference to Section	Screening	Baseline	Day 1	Week 4 [#]	Week 8 [#]	Week 12 [#]	Week 24 [#]	Week 36	Week 48	Week 60 & q12w onwards	End of Study/End of Treatment Section 7.6.2	Follow-up / Study Completion Evaluation Section 7.6.3	
Visit name		1	2	3	4	5	6	7	8	9				
Day of visit		-28 to -1	-7 to -1	Day 1	Day 28	Day 56	Day 84	Day 168	Day 252	Day 336				
Record (D)														
Survival (D)	7.6.3.1													X
Leukemia-free survival (D)	11.6.1.1													X
Bone marrow biopsy (optional) including percentage blasts (D)	7.3/8.3.1.2													X

Table 7-2 Laboratory assessment schedule

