3.11.3 Dynamic International Prognostic Scoring System (DIPSS)

The DIPSS can be used to assess a patient's prognosis as conditions change over time.

The risk level is assigned by the total score:

4 Change to protocol specified analyses

The definitions for the transfusion dependence at baseline, new onset of transfusion dependence and new transfusion independency (protocol v05 section 11.6.4.1) are not current. For the final analysis these definition have been updated as per IWG MRT 2013 ([section 3.6](#) of this SAP).

Clinical Study Report

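### The FACT-Lym repeated-measures model rests on a random intercept alone; an unstructured visit covariance is a cheap safeguard for its standard errors and visit means, and DIPSS status should be labelled as baseline

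*SAP*

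**What the plan says.** SAP 3.4.4 (Change in FACT-Lym scores) estimates change from baseline at each time point with a repeated-measures model. Patients need a baseline value and at least one later score. On the mean structure it says "Time on treatment time will be treated as a discrete variable to allow for a nonlinear relationship between PRO scores and time" and "Time, DIPSS status and baseline score (as a covariate) will be included in the model as fixed effects". On dependence between visits it says only "while the patient-specific intercept will be included as a random effect". It names no residual covariance, random slope, robust standard error or degrees-of-freedom method.

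Protocol Table 7-1 and the visit lists in Protocol 7.5.1.3, 7.5.1.7, 7.5.1.9 and 7.5.1.13 schedule FACT-Lym after baseline at weeks 4, 12, 24 and 48. It is not listed at the end-of-treatment or follow-up visits (Protocol 7.6.2.1, 7.6.3.1). SAP 3.4.4.1 plans no imputation.

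On the prognostic covariate, SAP 3.4.4 says "DIPSS status will be calculated as per the criteria given in section 3.11.3", and SAP 3.11.3 opens with "The DIPSS can be used to assess a patient's prognosis as conditions change over time". Only the score, not DIPSS status, is called baseline in the model statement.

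**The concern.** A random intercept with independent, equal-variance residuals is compound symmetry: every visit has the same variance, and every pair of visits has the same correlation, whether 8 weeks apart (weeks 4 and 12) or 44 weeks apart (weeks 4 and 48). The plan lets the mean take any shape over time but gives the covariance no such freedom.

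Three things could go wrong if the structure does not hold:

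- **Per-visit standard errors**, if the spread of change scores differs between visits.
- **Contrasts between visits**, if correlation fades with distance in time.
- **The visit means themselves**, if dropout depends on earlier scores. With nothing imputed and no questionnaire at end of treatment, this model is the only planned adjustment of the FACT-Lym means for dropout, and that adjustment works through the covariance.

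A smaller matter is that DIPSS status carries no time point in the model statement. Protocol 1.1 says "The DIPSS relies upon the same five variables as IPSS", and these include anemia and constitutional symptoms, which can move on treatment. Two programmers could read the covariate differently.

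**Working it through.** The documents state no SD, correlation or standard error for FACT-Lym change, so there is no planned figure to reproduce. The SDs and correlations below are assumptions, read as residual values after the model's covariates. From the documents come the visit weeks, the 2,238 patients enrolled (Protocol 4.1; an upper limit for this analysis) and the minimally important difference (MID) of 6.5 to 11.2 points for the FACT-Lym total (SAP 3.4.4).

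**1. Per-visit standard errors, no dropout.** The true SE at visit t is SD_t/√n. Compound symmetry pools the variances, so the model SE is √(mean of SD_t²)/√n at every visit. The ratio is therefore √(mean of SD_t²)/SD_t, and coverage of a nominal 95% interval is 2Φ(1.96 × ratio) − 1. Correlation does not enter.

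For SDs 12, 15, 17, 20, the mean variance is (144 + 225 + 289 + 400)/4 = 264.5, so the pooled SD is 16.3. At n = 600 the model SE is 16.3/24.5 = 0.66 at every visit, against true SEs of 0.49, 0.61, 0.69 and 0.82. A simulation (600 patients, 60 replicates) gave the same values.

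| Assumed SDs, weeks 4/12/24/48 | Model SE ÷ true SE | Coverage (%) |
|---|---|---|
| All equal | 1.00 / 1.00 / 1.00 / 1.00 | 95 / 95 / 95 / 95 |
| 16, 18, 20, 22 | 1.20 / 1.06 / 0.96 / 0.87 | 98 / 96 / 94 / 91 |
| 12, 15, 17, 20 | 1.35 / 1.08 / 0.96 / 0.81 | 99 / 97 / 94 / 89 |
| 14, 18, 22, 26 | 1.46 / 1.14 / 0.93 / 0.79 | 99.6 / 97 / 93 / 88 |

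With 30% dropout completely at random and fading correlation, equal SDs give a week 48 ratio of 0.95 (coverage about 94%). SDs 14 to 26 give 0.74 to 0.76 (85 to 86%) across the correlations tried.

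**2. The same error in points.** At n = 2,238, √n = 47.3. With SDs 12 to 20, the true week 48 SE is 20/47.3 = 0.42 and the model SE is 16.3/47.3 = 0.34. The 95% half-width is short by 1.96 × 0.08 ≈ 0.16 points.

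**3. Contrasts between visits, equal SDs, no dropout.** The variance of a difference between two visits is proportional to 1 − ρ, and the model uses one average ρ for all pairs. Suppose correlation is 0.8 per 8 weeks. The six pairwise values are 0.80 (lag 8 weeks), 0.72 (12), 0.57 (20), 0.51 (24), 0.37 (36) and 0.29 (44), with mean 0.543. For week 48 minus week 4 the SE ratio is √((1 − 0.543)/(1 − 0.293)) = √(0.457/0.707) = 0.80, giving coverage of about 89%. With 0.9 per 8 weeks the ratio is 0.77 and coverage 87%. For week 12 minus week 4 the error runs the other way: √(0.457/0.200) = 1.51.

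**4. Visit means under dropout.** Data were simulated (15 runs of 20,000 patients, true changes 8, 9, 9, 9) with the chance of leaving depending on the previous score and about 40% lost by week 48. The compound-symmetry model was fitted by maximum likelihood.

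| Truth | Bias at weeks 12 / 24 / 48 (points) |
|---|---|
| Compound symmetry true, SD 20 | −0.06 / −0.03 / −0.07 (simulation error) |
| Correlation 0.8 per 8 weeks, SD 20 | +1.0 / +0.2 / −2.2 |
| Correlation 0.8 per 8 weeks, SDs 14 to 26 | +1.1 / +1.9 / +0.9 |
| Correlation 0.8 per 8 weeks, SDs 14 to 26, no dropout | 0.00 / +0.01 / −0.03 |

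The unstructured model was not simulated. That it removes this bias when dropout depends only on observed scores follows from standard likelihood theory.

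**The case against.** The strongest reply is that nothing in the documents shows the assumption to be false. They give no SDs, so the 35% and 19% figures are one scenario among several, and with equal SDs and no dropout the per-visit standard errors are exactly right even when correlation fades. The SAP also does not say that residuals are independent with equal variance, so a programmer could add a residual structure within its wording. All of this stands. A reader might infer that the plan's per-visit error bars are wrong as a matter of fact; the documents support only that they can be.

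The stakes are also modest. Protocol 11.6.1 calls these analyses exploratory, Protocol 11 plans no tests, and raw by-visit summaries are planned alongside the model. An interval error of about 0.16 points is negligible against an MID of 6.5 to 11.2. This stands for precision, but less so for the means. The raw summaries use observed patients only, so they do not replace the model where dropout is informative.

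A reader might also infer that DIPSS is updated after treatment starts and so biases the estimated change. The documents do not support that. Protocol 5.2, Protocol 7.3 and Table 7-1 place risk-group assessment at screening, and no later risk-status collection is scheduled. Protocol 1.1 presents DIPSS as the score for patients assessed after diagnosis, which fits patients at entry. SAP 3.11.3 describes the instrument in general, and its scoring table is missing from the available text, so a time anchor there cannot be ruled out.

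**Conclusion.** The point holds in conditional form. On its natural reading, the model imposes equal variance and equal correlation on four visits spread over 44 weeks, although the design does not require this and the sample readily supports something freer. If SDs differ between visits, model-based per-visit standard errors will be wrong. Over the rising-SD patterns tried, with no dropout, they are 20 to 46% too large at week 4 and 13 to 21% too small at week 48. If correlation fades, contrasts between early and late visits are given too much precision. If dropout also depends on earlier scores, visit means can shift by up to about 2 points. That last effect matters most here, and it rests on strong assumed dropout and an assumed correlation pattern.

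None of this touches the primary safety objective. It is a low-cost improvement to an exploratory analysis. The DIPSS part is a wording clarification only.

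**What to change.** In SAP 3.4.4, replace the random intercept with an unstructured covariance across the four scheduled post-baseline visits (4 variances and 6 covariances). Name a fallback in advance if the fit fails: heterogeneous Toeplitz, or robust standard errors. Keep visit as a discrete factor.

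Add a rule selecting one record per patient per scheduled visit. It is needed because SAP 3.4.4.2 otherwise uses scheduled and unscheduled assessments alike; the ±7-day window in SAP 2.3 is a natural basis.

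In the same sentence, write *baseline DIPSS status*.

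The cost is a changed model statement, one record-selection rule and one added word. No new data are needed. Convergence was not tested, which is why the fallback should be stated.

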3.4.4.1 Handling of missing values/discontinuations in efficacy analyses

No imputation for missing data will be performed.

Patients with missing baseline assessments will be excluded from analysis where baseline value is required to compute the corresponding endpoint.

3.4.4.2 Center pooling

All data from all centers participating in this trial will be combined and analyzed together.

Unless specified otherwise, all assessments (scheduled and unscheduled) will be used for every patient in the analysis.

3.5 Safety evaluation

This section describes the planned statistical analyses for Sections 10, 12, 14, and 16 of the clinical study report.

Safety analysis will be based on safety population and will use the data collected during the study. Cut off for the safety reporting is end-of-treatment date + 28 days.

The following safety endpoints will be analyzed:

- Treatment-emergent AEs and serious adverse events (SAEs).
- AEs leading to study drug discontinuation.
- Adverse events of interest.
- Clinical laboratory values.
- Vital signs.
- Targeted physical examinations.
- 12-lead electrocardiograms (ECGs).

3.5.1 Adverse events

In this section the term adverse event or AE refers only to treatment-emergent AEs unless specified otherwise.

Only treatment emergent AEs will be summarized, i.e. events started after the first dose of study medication or events present prior to the first dose of study medication but increased in severity during study treatment based on PT, while all reported AEs will be included in listing.

The incidence of AEs will be tabulated by MedDRA (Medical Dictionary for Regulatory Activities) PT and SOC. Incidence of AEs will also be summarized by system organ class, severity (based on CTCAE grades version 3.0).

The same analysis will be repeated for SAEs regardless of drug relationship, drug related SAEs, AEs which CTCAE grade is 3 or 4 and for drug related AEs.

Deaths reportable as SAEs and non-fatal SAEs will be listed by patient and tabulated by type of AE.

Separate summaries for on-treatment and all on-study deaths (on-treatment and post-treatment) will be produced by system organ class and preferred term. All deaths will be listed and post treatment deaths will be flagged.

The most up to date MedDRA will be used for reporting AEs in the study. If a patient reported more than one AE with the same PT, the AE with the greatest severity will be presented. If a patient reported more than one AE within the same primary SOC, the patient will be counted only once with the greatest severity at the SOC level, where applicable.

Separate summaries will be provided for study medication related AEs, death, SAEs, other significant adverse events leading to discontinuation and AEs leading to dose adjustment. Non-serious adverse events will be listed separately.

For the legal requirements of ClinicalTrials.gov and EudraCT, two required tables on on-treatment adverse events which are not serious adverse events with an incidence greater than 5% and on on-treatment serious adverse events and SAE suspected to be related to study treatment will be provided by system organ class and preferred term on the safety set population.'

If for a same patient, several consecutive AEs (irrespective of study treatment causality, seriousness and severity) occurred with the same SOC and PT:

- a single occurrence will be counted if there is ≤ 1 day gap between the end date of the preceding AE and the start date of the consecutive AE
- more than one occurrence will be counted if there is > 1 day gap between the end date of the preceding AE and the start date of the consecutive AE

For occurrence, the presence of at least one SAE / SAE suspected to be related to study treatment / non SAE has to be checked in a block e.g., among AE's in a ≤ 1 day gap block, if at least one SAE is occurring, then one occurrence is calculated for that SAE.

The number of deaths resulting from SAEs suspected to be related to study treatment and SAEs irrespective of study treatment relationship will be provided by SOC and PT.

The number of deaths resulting from SAEs suspected to be related to study treatment and SAEs irrespective of study treatment relationship will be provided by SOC and PT

The relationship or association of the AE to a study drug will be characterized as Suspected or Not suspected.

Any missing onset date, causality, or severity must be queried for resolution. Unresolved missing values will be imputed according to the following:

- An unresolved missing causality will be imputed by being suspected.
- An unresolved missing severity will be left as missing in the AE tables.
- An unresolved missing onset date will be imputed by the Study Day 1, which will force the AE to be treatment emergent, with the following exceptions:
 - If the stop/resolution date is prior to Study Day 1, the AE will then be considered as not being treatment-emergent.
 - If both the month and day are missing, and the last day of the year is prior to Study Day 1, the AE will then be considered as not being treatment-emergent.
 - If only the day is missing, and the last day of the month is prior to Study Day 1, then the AE will be considered as not being treatment-emergent.

Date imputation for AEs will be imputed according to Novartis conventions described in [RAP Module 8].

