3.3 Study endpoints

3.3.1 Safety

- Safety and tolerability will be collected by monitoring the frequency, duration and severity of all grade AEs by the National Cancer Institute CTCAE v. 3.0, performing physical exams (PE), and evaluating changes in vital signs (VS), ECOG performance status (PS), electrocardiograms (ECGs) and serum chemistry, hematology results.
- Grade 3 and 4 AEs, Serious Adverse Events (SAEs).
- Change in laboratory values from Baseline to End of Treatment (serum chemistry and hematology).
- Changes in weight from Baseline to each assessment point and at end of treatment.
- Cardiac function as assessed by electrocardiograms (ECGs).

- Changes in vital signs.

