9.2.2 Reporting

To ensure patient safety, every SAE, regardless of suspected causality, occurring after the patient has provided informed consent and until at least 28 days after the patient has stopped study treatment must be reported to Novartis within 24 hours of learning of its occurrence. Any SAEs experienced after this 28 days period should only be reported to Novartis if the investigator suspects a causal relationship to the study treatment. Recurrent episodes, complications, or progression of the initial SAE must be reported as follow-up to the original

episode within 24 hours of the investigator receiving the follow-up information. An SAE occurring at a different time interval or otherwise considered completely unrelated to a previously reported one should be reported separately as a new event.

Information about all SAEs is collected and recorded on the Serious Adverse Event Report Form. The investigator must assess and record the relationship of each SAE to each specific study treatment (if there is more than one study treatment), complete the SAE Report Form in English, and send the completed, signed form by fax within 24 hours to the oncology Novartis DS&E department.

The telephone and telefax number of the contact persons in the local department of DS&E, specific to the site, are listed in the investigator folder provided to each site. The original copy of the SAE Report Form and the fax confirmation sheet must be kept with the case report form documentation at the study site.

Follow-up information is sent to the same contact(s) to whom the original SAE Report Form was sent, using a new SAE Report Form stating that this is a follow-up to the previously reported SAE and giving the date of the original report. Each re-occurrence, complication, or progression of the original event should be reported as a follow-up to that event regardless of when it occurs. The follow-up information should describe whether the event has resolved or continues, if and how it was treated, whether the blind was broken or not, and whether the patient continued or withdrew from study participation.

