3.4.1 Primary endpoints

3.4.1.1 Variables

The analysis of the primary endpoint will be performed on the incidence by patients of **treatment-emergent AEs** considering or not certain AEs characteristics (e.g. relationship to study medication, severity).

Incidence of a given AE is defined as the ratio of total number of patients experiencing the given AE at least once (defined by its preferred term [PT]) divided by the total number of patients at risk (i.e. part of the safety set).

A treatment-emergent AE is an AE that first occurs or worsens during treatment (including the 28 days following last treatment administration).

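### The AE onset rule in SAP 3.5.1 overrides a recorded later month or year with Study Day 1, and its precedence over RAP Module 8 is not stated

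*SAP*

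**What the plan says.** SAP 3.5.1 requires a query for any missing AE onset date. If the query fails, the default is: "An unresolved missing onset date will be imputed by the Study Day 1, which will force the AE to be treatment emergent". Three exceptions follow.

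- By stop date: "If the stop/resolution date is prior to Study Day 1, the AE will then be considered as not being treatment-emergent".
- By year: "If both the month and day are missing, and the last day of the year is prior to Study Day 1", the AE is not treatment-emergent.
- By month: the same holds when only the day is missing and the recorded month ended before Day 1.

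The section closes with a second instruction: "Date imputation for AEs will be imputed according to Novartis conventions described in" RAP Module 8. The content of that module is not in the protocol or SAP, and no order of precedence is given.

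The primary endpoint depends on treatment-emergent status. SAP 3.4.1.1 defines it thus: "A treatment-emergent AE is an AE that first occurs or worsens during treatment (including the 28 days following last treatment administration"). Incidence is the number of patients with the preferred term at least once, divided by the safety set.

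For the registry tables, SAP 3.5.1 also counts occurrences. For consecutive AEs with the same system organ class and preferred term, "a single occurrence will be counted if there is" a gap of at most one day between the end of one and the start of the next; a longer gap gives a further occurrence.

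**The concern.** The second and third exceptions only make sense if the word missing includes partial dates. All three look backwards, and none keeps a recorded month or year that lies after Day 1. The default is a sensible cautious choice when the known parts could include Day 1. When they cannot, the imputed date contradicts what the site recorded.

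The SAP treats other dates differently: for partial dose end dates (SAP 3.2, Cases 2 to 4) it uses the known year and month.

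At stake are the registry occurrence counts, the treatment-emergent status of a small group of late events, and the agreement between derived onset days and recorded dates. Because the section also points to RAP Module 8, two programmers could derive different onset dates from the same record.

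**Working it through.** The plan states no figure to reproduce: the study is descriptive, with no sample size or power calculation (SAP 3.9). The check applies the written rule to examples and compares it with the first possible day of the recorded month or year.

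**Inputs.** The default, exceptions and one-day-gap rule come from SAP 3.5.1; the 28-day window from SAP 3.4.1.1; the follow-up visit at 28 to 37 days after last dose from Protocol 7.6.1. The dates are invented: Day 1 = 11 Mar 2013, last dose = 20 Jun 2014 (Day 467), window end = Day 467 + 28 = Day 495 (18 Jul 2014).

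**Step 1: onset day and status.** TE means treatment-emergent.

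| Recorded onset | Stop date | Written rule | First possible day |
|---|---|---|---|
| Feb 2013 | none | not TE | not TE |
| Mar 2013 | 20 Mar 2013 | Day 1, TE | Day 1, TE |
| Sep 2013 | 25 Sep 2013 | Day 1, TE | Day 175, TE |
| 2014 | 10 Feb 2014 | Day 1, TE | Day 297, TE |
| Jul 2014 | 25 Jul 2014 | Day 1, TE | Day 478, TE |
| Aug 2014 | 20 Aug 2014 | Day 1, TE | Day 509, not TE |

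Status differs only in the last row, where the whole month lies after Day 495. For onsets within treatment, or in a month that straddles the window end, the patient counts either way. The derived onset day is wrong in each of the last four rows. The interval to the stop date becomes, for example, 199 days instead of at most 199 − 175 + 1 = 25 for September 2013.

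**Step 2: occurrences.** Take one preferred term with a first episode on 1–5 May 2013 and a second recorded as Sep 2013, ending 25 Sep 2013. The written rule makes the second run from 11 Mar to 25 Sep 2013. It then contains the first, so 1 occurrence is counted. With 1 Sep 2013 as the start, the gap from 5 May exceeds one day and 2 are counted. Moving a start earlier can join blocks but never split them, so this error goes in one direction.

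**Step 3: how often status could change for events found at the follow-up visit.** For an onset k days after last dose (k = 29 to 37), a day-missing date is provably after the window only if the first of its month falls on days 29 to k. That is k − 28 candidate days, on average (1 + 2 + … + 9)/9 = 5. With 12 month starts per 365 days, the share is 5 × 12/365 = 0.164. If only the year is known, it is 5 × 1/365 = 0.0137. Enumerating every last-dose date over four years gave 16.4% and 1.4%. These are shares of partial dates in that nine-day band, not of all AEs.

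**Step 4: other late events.** Protocol 9.2.2 says: "Any SAEs experienced after this 28 days period should only be reported to Novartis if the investigator suspects a causal relationship". A case like August 2014, at least 42 days after last dose (10 + 31 + 1), would most plausibly arrive by this route. The passage requires a report to the sponsor's safety department; it does not say that the event enters the analysis database.

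**The case against.** The strongest reply is that RAP Module 8 may already handle partial dates. On that reading the SAP bullets settle only treatment-emergent status, which is all the exceptions mention, and the module supplies the date. This is possible, but the default bullet itself says that the onset date is imputed, so the text is at best ambiguous. What stands is that the Day 1 shift is the literal reading, not an established fact about the programming.

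The second reply is that the default errs towards inclusion, as does the neighbouring rule that treats missing causality as suspected. That is a fair defence where the known parts are compatible with Day 1. It does not cover occurrence counts, where the rule errs towards fewer events.

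The third reply concerns reach, and most of it stands. Required AE recording ends 28 days after last dose (Protocol 9.1.1), collection stops after Study Completion (Protocol 4.1), the safety cut-off is end of treatment + 28 days (SAP 3.5), and queries come first. A reader might infer that post-treatment events enter the primary tables in any number. The documents do not support that; only the narrow group in Steps 3 and 4 can be misclassified.

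A reader might also infer that reported AE durations will be inflated. Protocol 3.3.1 does list "monitoring the frequency, duration and severity of all grade AEs", but neither protocol 11.5 nor the SAP plans an AE-duration table.

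**Conclusion.** The concern holds in a limited form. As written, the rule discards recorded date information, and its relation to RAP Module 8 is unresolved.

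- Registry occurrence counts can only be lowered by the merging of episodes. Patient-level incidence is untouched by merging.
- An event whose known month or year lies wholly after last dose + 28 days is classed as treatment-emergent. The routes are onsets on days 29 to 37 found at the follow-up visit (about 16.4% of those with the day missing, 1.4% of those with only the year) and late suspected SAEs, if these are in the database.
- Because SAP 2.3 works in study days, a listing built on the derived onset would show Day 1 for an event known to be later.

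Patient-level incidence does not change for partial dates within treatment or overlapping the 28-day window. The documents give no number of partial onset dates left after queries, so the number of affected records cannot be estimated. Multiplying 2238 patients by an assumed AE rate and an assumed share of partial dates would count dates moved, not events misclassified. The conclusion assumes that the bullets are applied as written; if RAP Module 8 governs instead, the conflict still has to be resolved.

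**What to change.** Amend SAP 3.5.1 as follows, keeping the three existing exceptions.

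1. Use Study Day 1 only when the onset date is fully missing or its known parts are compatible with Day 1.
2. Otherwise impute the first possible day of the known month or year.
3. Class the AE as not treatment-emergent when that day is later than last dose + 28 days. A month that straddles the window end stays treatment-emergent, which keeps the cautious direction.
4. State that this rule prevails over RAP Module 8 for AE onset dates where the two differ. Do not delete the reference without seeing the module, since it may hold other conventions that are needed.

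The first possible day can still be early by up to the length of the known month or year, so some merging of episodes may remain, but the date no longer contradicts the record. The cost is SAP wording and a few lines of derivation code, with no new data. Treatment-emergent counts may fall slightly and registry occurrence counts may rise.
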